### 17.6.2 Reporting Adverse Events

Routine AEs occurring between the start date of intervention until 30 days after the last intervention, or until the event has resolved, the study participant is lost to follow-up, the start of a new treatment, or until the study investigator assesses the event(s) as stable or irreversible, will be reported. New information will be reported after it is received.

#### Guidelines for Routine Adverse Event Reporting for Phase 1 Studies (Regardless of Expectedness)

Attribution	Grade 1	Grade 2	Grade 3	Grade 4
Unrelated	X	X	X	X
Unlikely	X	X	X	X
Possible	X	X	X	X
Probable	X	X	X	X
Definite	X	X	X	X

#### Guidelines for Routine Adverse Event Reporting for Pilot, Phase 2, and Phase 3 Studies (Regardless of Expectedness)

Attribution	Grade 1	Grade 2	Grade 3	Grade 4
Unrelated			X	X
Unlikely			X	X
Possible	X	X	X	X
Probable	X	X	X	X
Definite	X	X	X	X

## 17.7 Serious Adverse Events

A serious adverse event (SAE) is any adverse event (experience) that in the opinion of either the investigator or sponsor results in **ANY** of the following:

- Death.
- A life-threatening adverse event (experience). Any AE that places a participant or participants, in the view of the Investigator or sponsor, at immediate risk of death from the reaction as it occurred. It does NOT include an AE that, had it occurred in a more severe form, might have caused death.
- Inpatient hospitalization or prolongation of existing hospitalization (for > 24 hours).
- A persistent or significant incapacity or substantial disruption of the ability to conduct normal life functions.
- A congenital anomaly or birth defect.
- Important Medical Event (IME) that, based upon medical judgment, may jeopardize the participant and may require medical or surgical intervention to prevent one of the outcomes listed above.

### 17.7.1 Reporting Serious Adverse Events

All new SAEs occurring from the date the participant signs the study consent until 30 days after the last intervention or a new treatment is started, whichever comes first, will be reported. The Roswell Park SAE Source Form is to be completed with all available information, including a brief narrative describing the SAE and any other relevant information.

SAEs occurring after the 30 day follow-up period that the investigator determines to be possibly, probably, or definitely related to the study intervention should be reported.

SAEs identified as an Unanticipated Problem by the Investigator must be reported. Please refer to **Section 17.10** for details on reporting Unanticipated Problems.

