## 8 STUDY ENDPOINTS

### 8.1 Primary Endpoints

- The primary safety endpoints are frequency of grade 3 or 4 AEs considered to be probably or definitely related to the treatment regimen.
- Evaluate kinetics of viral load expressed as Ct values in nasopharyngeal swab samples in the course of treatment and Days 7 and 14. (40)

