## 9 STUDY DESIGN

The antiviral efficacy of the combination of interferon alpha-2b and rintatolimod will be evaluated by administering fixed doses of each drug. Subjects will receive 1 day of the combination (Day 1), followed by 1 day of observation and the same regimen on Day 3 (or Day 4), according to the safe established dosing levels (see Table 1). During this time, subjects will be monitored continuously for safety (refer to Section 19.2.1). As the standard of care therapy for COVID-19 is evolving, all patients will receive optimal standard of care that will be administered concurrently with the study drug regimen. In a double-blind, randomized, multi-center, placebo-controlled trial of intravenous remdesivir in adults hospitalized with COVID-19 with evidence of lower respiratory tract involvement, remdesivir treatment resulted in shortening the time to recovery by 4 days (43). Though 14-day survival was greater in remdesivir recipients, the difference was not statistically significant (43). Adults hospitalized with COVID-19 with evidence of lower respiratory tract involvement will be offered remdesivir through an EUA if and when this drug is available to us. If we're not able to offer remdesivir to all patients based on drug availability, we expect a similar proportion of patients in the study drug and control arms to have received remdesivir, and the effect of remdesivir on study endpoints will be evaluated in an exploratory fashion.

Roswell Park Protocol No.: I-659920

In a multi-center controlled, open-label trial comparing a range of possible treatments in patients who were hospitalized with COVID-19, patients were randomly assigned to receive oral or intravenous dexamethasone (6 mg daily) for up to 10 days or to receive usual care alone (44). Overall, 482 patients (22.9%) in the dexamethasone group and 1110 patients (25.7%) in the usual care group died within 28 days after randomization ( $p < 0.001$ ). The survival benefit of dexamethasone was observed among patients receiving either invasive mechanical ventilation or oxygen alone at randomization but not among those receiving no respiratory support. Based on these results, dexamethasone (6 mg/day) will be given as standard of care to patients admitted with COVID-19 who require supplemental oxygen.

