#### **10.2.2 Definition of DLT**

Treatment-related DLTs will be defined as the following events that occur between Day 1 to Day 7 that are considered possibly, probably, or definitely treatment-related:

- Grade 4 hematologic toxicity.
- Grade 3 hematologic toxicity with exception of transient leukopenia, neutropenia, lymphopenia, thrombocytopenia without bleeding, or anemia lasting 7 days or less.
- Grade 4 non-hematologic toxicities, with exception of asymptomatic increased LDH or lipase or amylase.
- Grade 3 non-hematologic toxicities with exception of nausea, vomiting, diarrhea, or flu-like symptoms that are controlled by optimal supportive management.

Distinguishing clinical manifestations of COVID-19 from treatment-related DLT can be difficult because they can overlap. Manifestations of COVID-19 present at baseline (e.g., fever, shortness of breath) that are unchanged after the study regimen is begun will not be considered DLT. Worsening of these manifestations can be due to COVID-19 or treatment-related, and unless there is a specific well defined unrelated cause, all AEs that are at least possibly related to the study regimen that meet one of the criteria for DLT based on CTCAE severity will be considered DLT.

In patients who received recent chemotherapy, radiation, and/or immunotherapy toxicities from recent chemotherapy would be known to the primary oncologist, and we would interpret AEs attributed to the study regimen with this knowledge in mind. For example, if a patient received cytotoxic chemotherapy known to cause leukopenia prior to development of COVID-19, development of leukopenia following initiation of study therapy will not be considered treatment-related, depending on the expected degree and duration of leukopenia following chemotherapy.

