#### **10.2.3 Toxicity Management**

The toxicity of high dose interferon (20 million units/m^2/d) has been established by Kirkwood et al in a number of trials. Most notable was the E1684 trial (47) where HDI (20 million units/m^2/d) was administered daily for 5 days x 4 weeks. In that trial (n=143), grade 3 toxicities were 67%, grade 4 toxicities were 9% (mainly constitutional and neurologic), and there were 2 treatment related mortalities (grade 5) due to hepatotoxicity. The proportion of Grade 3 and 4 toxicities in that trial were 48.2% for constitutional toxicities (defined as ‘worst grade of any constitutional toxicity, including fever, chills, flu-like symptoms, fatigue, malaise, and diaphoresis), and 66% for non-constitutional toxicities (23.8% for myelosuppression, 13.9% for hepatotoxicity, 28% for neurological toxicity).

Roswell Park Protocol No.: I-659920

While the combination of HDI and rintatolimod may lead to synergistic additive side effects, we will monitor subject toxicities for unexpected increases in constitutional symptoms, myelosuppression, hepatotoxicity, and neurological toxicity. We will focus on monitoring for grade 3 or greater treatment related hematologic toxicities, and grade 4 or greater treatment related non-hematologic toxicities. A non-informative prior distribution of SAEs will be utilized to develop the safety stopping rules (details in Section 19).

To our knowledge, the combination of HDI and rintatolimod has not been tested previously in patients with COVID-19. Therefore, we may observe adverse events that were not observed in trials of cancer and specific adverse events may be more severe in patients with COVID-19. One possibility is worsening of acute lung injury or systemic inflammatory response. Though the protocol does not specify specific treatments for such AEs, agents used for cytokine release syndrome, e.g. Tocilizumab, or JAK2, TNF $\alpha$ , IL-1 inhibitors, may be used, based on physician judgment.

- **Gastrointestinal Toxicity**

- Nausea and/or vomiting should be controlled with adequate antiemetic therapy. Prophylactic antiemetic therapy can be used at the discretion of the investigator/sub-investigator. Subjects are encouraged to take plenty of oral fluids.

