## **16 MEASUREMENT OF EFFECT**

### **16.1 Primary Endpoints**

- The **primary safety** endpoints are frequency of grade 3 or 4 AEs considered to be possibly, probably, or definitely related to the treatment regimen.
- Evaluate kinetics of viral load in nasopharyngeal swabs based on quantitative PCR in the course of treatment and Days 7, and 14.

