### **Primary Endpoint**

- The primary safety endpoint is the frequency of grade 3 or 4 AEs considered to be possibly, probably, or definitely related to the treatment regimen.

**Phase IIa.** The Phase IIa component of the trial is designed to be a single arm trial of IFN $\alpha$  (at MTD, if reached, otherwise at 20 MU/M) + rintatolimod along with the best available standard of care. Using each patient's baseline nasopharyngeal viral load, we will evaluate to what extent the study regimen reduces viral load relative historical institutional benchmarks. The sample size will be n=10.

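### Grade 5 events are missing from all four primary safety endpoint statements and from the DLT list, and SAE reporting can close early at an undefined new treatment

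*Combined protocol and SAP*

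**What the plan says.** **Primary safety endpoint.** It is stated four times.
- Section 8.1: "frequency of grade 3 or 4 AEs considered to be probably or definitely related to the treatment regimen".
- Section 16.1: "frequency of grade 3 or 4 AEs considered to be possibly, probably, or definitely related to the treatment regimen".
- Section 19.1, Phase I: "The primary safety endpoint is the frequency of grade 3 or 4 AEs", with possible attribution included.
- Section 19.1, Phase IIa: the same grades, with probable or definite attribution only.

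**DLTs.** Section 10.2.2 lists four categories: grade 4 and qualified grade 3 hematologic events, and grade 4 and qualified grade 3 non-hematologic events. The highest non-hematologic category reads "Grade 4 non-hematologic toxicities, with exception of asymptomatic increased LDH or lipase or amylase". The later sentence on events that overlap with COVID-19 brings in only events that satisfy one of these listed criteria. Section 19.2.1 uses the count: one DLT in three patients adds three more, and two among three to six stops escalation.

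**Where grade 5 does appear.** Section 10.2.3 directs monitoring at grade 3 or above (hematologic) and grade 4 or above (non-hematologic). For the cited trial of interferon at 20 million units/m² it reports that "there were 2 treatment related mortalities (grade 5) due to hepatotoxicity".

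**Reporting windows.** Section 17.7.1 reports SAEs from consent "until 30 days after the last intervention or a new treatment is started, whichever comes first". Its next paragraph adds related SAEs that occur once the 30-day follow-up period is over. For routine AEs, 17.6.2 gives a list of alternative end points that includes "the study participant is lost to follow-up, the start of a new treatment". Section 17.8 has a similar list for follow-up of related SAEs. No section defines a new treatment.

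**The concern.** Safety is a primary objective, and the 3+3 rule acts on very small counts, so one uncounted event can change a decision. A definition that stops at grade 4 leaves the most severe related outcome out of both the headline frequency and the escalation count. The SAE window raises a related problem. It can close on an event that the protocol never defines, in patients who are expected to receive other therapies. Both defects, where they act, lower the recorded toxicity.

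**Working it through.** The plan gives no figure to reproduce here. The check is a reading of the definitions, followed by illustrations of their effect.

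**1. Grade range by location**

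| Location | Highest grade covered |
|---|---|
| 8.1, primary safety endpoint | 4 |
| 16.1, primary safety endpoint | 4 |
| 19.1 Phase I, primary safety endpoint | 4 |
| 19.1 Phase IIa, primary safety endpoint | 4 |
| 10.2.2, all four DLT categories | 4 |
| 17.6.2, both routine AE tables | 4 |
| 10.2.3, monitoring sentence | 5 (open-ended) |

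Grade 5 is in 0 of 4 endpoint statements and 0 of 4 DLT categories.

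**2. Effect on one dose level of three patients (19.2.1 rule)**

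| Events | Literal count and action | Count and action if grade 5 is included |
|---|---|---|
| One related death | 0/3, escalate | 1/3, add three |
| One related death and one other DLT | 1/3, add three | 2/3, do not escalate |

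**3. Probability of escalating.** With counted DLT rate p, P(escalate) = (1−p)³ + 3p(1−p)² × (1−p)³. The true rates and the grade 5 share below are assumptions. A share s left uncounted replaces p by p(1−s).

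| True rate of grade 3–5 DLT-type events | All counted | s = 10% | s = 25% | s = 50% |
|---|---|---|---|---|
| 20% | 0.71 | 0.75 | 0.81 | 0.91 |
| 33% | 0.43 | 0.50 | 0.61 | 0.78 |
| 40% | 0.31 | 0.38 | 0.49 | 0.71 |

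**4. How often it might arise.** The cited trial had 2 deaths in 143 patients, or 1.4%. At most 6 + 10 = 16 Main Cohort patients (top dose level plus Phase IIa) would receive 20 MU/m². At 1.4% each, P(at least one) = 1 − (141/143)¹⁶ = 0.20, or 0.13 for the ten Phase IIa patients alone. This only gives scale. The cited course was daily for 5 days over 4 weeks, against two infusions here, and its patients did not have COVID-19.

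**5. The SAE window.** Let L be the day of the last infusion and T the day a new treatment starts.
- The general clause runs from consent to the earlier of T and L + 30.
- The related-SAE clause starts after L + 30.
- If T comes before L + 30, a related SAE between T and L + 30 is in neither clause.

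In the Main Cohort L is Day 3 or 4, so L + 30 is Day 33 or 34. The gap is that day minus T, and T depends on the missing definition.

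**6. Expansion Cohort.** The second infusion is on Day 3 or 4. Up to ten more follow, 3 to 4 days apart, so the last falls between Day 3 + 30 = 33 and Day 4 + 40 = 44. Thirty days later is Day 63 to 74. Section 7 follows patients only to Day 30 after initiation.

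**The case against.** The strongest reply is that deaths are well covered elsewhere. Death is the first SAE criterion in 17.7, death within 30 days is a secondary endpoint (8.2, 16.2, 19.1), related unexpected fatal events go to the FDA within 7 days (17.10), and the data safety monitoring committee reviews safety data. This stands. A reader might infer that the worst events are lost from the trial, and the documents do not support that. They are missing from one frequency and one count. The 30-day death endpoint is itself not firm, because the Appendix F calendars list survival follow-up through Day 14.

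A second reply is that investigators would treat a related death as a DLT anyway, or would already have recorded the same event at grade 3 or 4. That is likely in practice. But the protocol does not say how an event that progresses to death is counted, and an escalation rule should not depend on it.

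On the reporting window, three stronger readings are tempting.
- *Reporting stops when patients deteriorate.* Dexamethasone "will be given as standard of care to patients admitted with COVID-19 who require supplemental oxygen", and Section 10 lists tocilizumab within standard of care. Both are described as background therapy, so they need not be a new treatment. Section 32.1.5 allows continued anticancer therapy, so resuming it is not clearly new either. The defect is a missing definition.
- *Routine AEs have the same cut-off.* Section 17.6.2 lists alternatives and does not say that the earliest governs. AE recording on Days 7 and 14 carries no such exception.
- *Only 4 of about 34 days (12%) are kept.* That needs a Day 4 start and a definition that the documents do not give.

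DLTs also have their own Day 1 to Day 7 window, with no new-treatment exception. What remains is a narrow gap for related SAEs. Unanticipated Problem and FDA reports close it only in part, since both require the event to be unexpected.

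**Conclusion.** The grade 5 omission is complete on the text: no primary safety endpoint statement and no DLT category includes it, in conflict with the monitoring range in 10.2.3. Read literally, one related death moves a three-patient level from 1/3 to 0/3. At an assumed true rate of 33%, the chance of escalating rises from 0.43 to between 0.50 and 0.78 if grade 5 makes up 10% to 50% of the events. These figures assume that a fatal event is recorded only at grade 5 and that nobody overrides the rule. The primary safety frequency has no numeric threshold, so no formal test result changes there. What changes is the reported frequency.

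The reporting gap in 17.7.1 is real but secondary. It affects related SAEs between an undefined new treatment and the 30-day mark, and its length cannot be determined from the documents.

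**What to change.** 1. In 8.1, 16.1 and both parts of 19.1, replace grade 3 or 4 with grade 3 or higher (including grade 5). The same edit should settle the attribution difference: 8.1 and Phase IIa leave out possibly related events, while 16.1 and Phase I count them.
2. Reconcile the grade range in 10.2.2 with those statements and with 10.2.3, and bring the routine AE tables in 17.6.2 into line.
3. In 17.7.1, remove the new-treatment cut-off, or state that concurrent COVID-19 standard of care and resumed anticancer therapy do not trigger it. Align 17.6.2 and 17.8.

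The cost is a protocol amendment and a modest increase in reported events. For Expansion Cohort patients given additional infusions, SAE collection would run past the Day 30 follow-up in Section 7, to about Day 63 to 74 after the maximum of 12. Section 7 and the calendars would need to allow for this.

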## 17.8 Follow-Up for Serious Adverse Events

All related SAEs should be followed to their resolution, until the study participant is lost to follow-up, the start of a new treatment, or until the study investigator assesses the event(s) as stable or irreversible. New information will be reported when it is received.

## 17.9 Unanticipated Problems

An Unanticipated Problem (UP) is any incident, experience, or outcome that meets all of the following criteria:

- Unexpected (in terms of nature, severity, or frequency) given:
  - The research procedures that are described in the study-related documents, including study deviations, as well as issues related to compromise of participant privacy or confidentiality of data.
  - The characteristics of the participant population being studied.
- Related or possibly related to participation in the research (possibly related means there is a reasonable possibility that the incident, experience, or outcome may have been caused by the procedures involved in the research).

Roswell Park Protocol No.: I-659920

- Suggests that the research places participants or others at a greater risk of harm (including physical, psychological, economic, or social harm) than was previously known or recognized and if in relation to an AE is also deemed Serious per Section 17.7.

### **17.9.1 Reporting Unanticipated Problems**

The Reportable New Information (RNI) Form will be submitted to the CRS Quality Assurance (QA) Office within 1 business day of becoming aware of the Unanticipated Problem. After review, CRS QA Office will submit the RNI to the IRB.

When becoming aware of new information about an Unanticipated Problem, submit the updated information to CRS QA Office with an updated Reportable New Information Form. The site Investigator or designated research personnel will report all unanticipated problems to the IRB in accordance with their local institutional guidelines.

### **17.10 FDA Reporting**

When Roswell Park is the IND holder the following describes the FDA reporting requirements by timeline for AEs and new safety findings that meet the criteria outlined below:

#### **Within 7 Calendar Days**

Any adverse event that meets ALL the following criteria:

- Related or possibly related to the use of the study drug.
- Unexpected; and
- Fatal or life-threatening.

#### **Within 15 Calendar Days**

Any adverse event that meets ALL the following criteria:

- Related or possibly related to the use of the study drug.
- Unexpected; and
- Serious but not fatal or life-threatening.

Or, meets ANY of the following criteria:

- A previous adverse event that is not initially deemed reportable but is later found to fit the criteria for reporting (report within 15 days from when event was deemed reportable).
- Any findings from other studies, including epidemiological studies, pooled analysis of multiple studies, or other clinical studies conducted with the study drug that suggest a significant risk in humans exposed to the drug.
- Any findings from animal or in vitro testing that suggest a significant risk for human participants including reports of mutagenicity, teratogenicity, or carcinogenicity or reports of significant organ toxicity at or near the expected human exposure.
- Any clinically important increase in the rate of occurrence of a serious, related or possibly related adverse event over that listed in the protocol or investigator brochure.

Roswell Park Protocol No.: I-659920

Sponsors are also required to identify in IND safety reports, all previous reports concerning similar adverse events and to analyze the significance of the current event in the light of the previous reports.

## **Reporting Process**

The principal investigator or designee will complete and submit a FDA Form 3500A MedWatch for any event that meets the above criteria. Forms will be submitted to the CRS QA Office via email to [contact].

## **18 DATA MANAGEMENT AND CONFIDENTIALITY**

### **18.1 Data Collection**

Full build studies are managed by Roswell Park CRS Data Management for analysis by Roswell Park Biostatisticians. All electronic case report form (eCRF) data are captured for these studies.

Data management activities are performed using a CTMS system that enables the collection, cleaning and viewing of clinical trial data. CRS data management designs the study-specific database and facilitates development by the Information Technology team. Once the database design is approved by the Investigator, Statistician, and Clinical Research Coordinator, the database is put into production and data entry can begin. Data can be entered and changed only by those with the rights to do so into the eCRFs.

### **18.2 Maintenance of Study Documents**

Essential documents will be retained per Roswell Park's policy for 6 years from the study termination date. These documents could be retained for a longer period, however, if required by the applicable local regulatory requirements or by an agreement with Roswell Park.

